**Definition of On-Treatment period:**

For the Induction Phase, the on-Treatment period is defined as the time from the first dose of induction chemotherapy treatment through the earliest of (the date of the last dose of Induction chemotherapy + 30 days, start day of new anti-cancer drug therapy – 1 day, date of Maintenance Phase study treatment start – 1 day).

For subjects randomized to the avelumab arm or the control arm and receive chemotherapy, the on-treatment period is defined as the time from the first dose of randomized treatment through the earliest of (last dose of study treatment + 30 days, start day of subsequent anti-cancer drug therapy – 1 day). For subjects randomized to the control arm and receive BSC-only, study treatment is considered to start on the day of the Week 1 Day 1 assessment visit and end on the earliest date given from among the following: date given on the Study Termination eCRF page and date of death. Thus, the on-treatment period for these subjects is defined as the time from the Week 1 Day 1 assessment visit to the earlier of (end of assessment date + 30 days, start of new anti-cancer drug therapy – 1 day).

The date of subsequent anti-cancer drug therapy is derived as outlined in Section 13.2.

**Standard derivations and reporting conventions:**

The following conversion factors will be used to convert days into weeks, months or years:

1 week = 7 days, 1 month = 30.4375 days, 1 year = 365.25 days.

Demographics and physical measurements:

- Age (years) for use in Induction Phase demographics:
  - (date of given informed consent - date of birth + 1) / 365.25

- In case of missing day, day only: Age [years]: (year/month of given informed consent – year/month of birth) / 12
- In case only year of birth is given: Age [years]: (year of given informed consent - year of birth)

The integer part of the calculated age will be used for reporting purposes.

- Age (years) for use in Maintenance Phase demographics:
  - (date of randomization - date of birth + 1) / 365.25
  - In case of missing day, day only: Age [years]: (year/month of randomization – year/month of birth) / 12
  - In case only year of birth is given: Age [years]: (year of randomization - year of birth)

The integer part of the calculated age will be used for reporting purposes.

- BMI (kg/m^2) = weight (kg) / [height (m)].
- BSA (m^2) = ([height (cm) × weight (kg)] / 3600)0.5

Reporting conventions are detailed in the sub-section titled “Presentation of continuous and qualitative variables”, earlier in this section.

#### **Unscheduled visits:**

Data collected at unscheduled visits will be included and analyzed for both safety and efficacy analyses in the same fashion as the data collected at scheduled visits except where otherwise noted. Descriptive statistics (mean, StDev, median, minimum, maximum and quartiles) by nominal visit or time point for safety endpoints such as laboratory measurements, ECGs, and vital signs, will include only data from scheduled visits.

#### **Summary statistics over time:**

For descriptive statistics over time by nominal visit or time point for HRQoL data and safety endpoints (laboratory, ECG and vital signs), only those scheduled, per-protocol visits/time points that have at least 5 subjects in both treatment arms will be included in the summary tables and figures. The exception is Discontinuation/End-of-Treatment visit which will be included in the summary table/figure regardless of the number of subjects who may have completed visit. Tables for safety end-points will only summarize on-treatment records.

#### **Missing data and imputation rules:**

Unless otherwise specified in this SAP, all data will be evaluated as reported and no imputation of missing values will be done.

In all subject data listings imputed values will be presented. In all listings imputed information will be flagged.

Missing statistics, e.g. when they cannot be calculated, will be presented as 'nd' or 'n/a'. For example, if N=1, the measure of variability (StDev) cannot be computed and would be presented as 'nd'.

For laboratory assessments indicating that the sample tested below the lower limit of quantitation (LLOQ) for the analyte in question, half the lower limit of quantitation ( $\frac{1}{2}$ \*LLOQ) will be used as the analysis value. For laboratory assessments testing above the upper limit of quantitation (ULOQ), the analysis value will be imputed as  $\{ULOQ + 1 * (\text{the level of precision of ULOQ})\}$ . For example, if an assessment tests at a value ">7.0", the level of precision is 0.1 and the analysis value will be 7.1. The imputed analysis values will be used in all analyses (e.g. summary statistics) and will be used for determination of toxicity grading. Listings will present the standardized unit values as provided in the raw data, indicating the assessment value was not quantifiable (e.g. ">7.0").

Partial dates will be imputed as follows:

#### **Disease history**

Incomplete dates for disease history (initial diagnosis date, date of documented, locally advanced, inoperable or metastatic disease diagnosis, date of response or progression in prior treatment) will be imputed as follows:

- If the day is missing, it will be imputed to the 15th day of the month.
- If both day and month are missing and the year is prior to the year of the first study treatment, the month and day will be imputed as July 1st.
- If both day and month are missing and the year is same as the year of the first study treatment, the month and day will be imputed as January 1st.
- If the date is completely missing, no imputation will be performed.

#### **Adverse events**

Incomplete AE-related dates will be imputed as follows:

- If the AE onset date is missing completely, then the onset date will be replaced by the start of randomized treatment.
  - If only the day part of the AE onset date is missing, but the month and year are equal to the start of randomized treatment, then the AE onset date will be replaced by the start of randomized treatment. For example, if the AE onset date is --/JAN/2015, and randomized treatment start date is 15/JAN/2015, then the imputed AE onset date will be 15/JAN/2015.
  - If both the day and month of the AE onset date are missing but the onset year is equal to the start of randomized treatment, then the onset date will be replaced by the start of randomized treatment.
-

For example, if AE onset date is --/---/2014, and randomized treatment start date is 19/NOV/2014, then the imputed AE onset date will be 19/NOV/2014.

- In all other cases, the missing onset day or missing onset month will be replaced by 1.
- Incomplete stop date will be replaced by the last day of the month (if day is missing only), if not resulting in a date later than the date of subject's death. In the latter case, the date of death will be used to impute the incomplete stop date.
- In all other cases, the incomplete stop date will not be imputed.

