**Definition of treatment day:**

Treatment day is defined relative to the start date of study treatment within a given Treatment Phase. Treatment Day 1 is defined as the first day study treatment within a given Phase; Treatment Day -1 is defined as the day prior to the start of the given treatment. Treatment Day 0 is not defined. For example, for the Induction Phase, Treatment Day 1 is defined as the first day of Induction Phase chemotherapy and the day before is defined as Treatment Day -1. Similarly, for subjects randomized to active treatment during Maintenance Phase, Treatment Day 1 is defined as the day the first dose of Maintenance Phase study drug was given. For subjects randomized to receive BSC-only during Maintenance Phase, Treatment Day 1 is defined as the date of the Week 1 Day 1 assessment visit.

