#### **Prior/concomitant medication**

Incomplete prior/concomitant medication dates will be imputed as follows:

- If the medication date is missing completely, then the medication date will be replaced by the start of Induction Phase treatment.
- If the day of medication date is missing, but the month and year are equal to the start of Induction Phase treatment, then the medication date will be replaced by the start of Induction Phase treatment. For example, if the medication start date is --/JAN/2015, and Induction Phase treatment start date is 15/JAN/2015, then the imputed medication start date will be 15/JAN2015.
- If both the day and month of medication start date are missing but the start year is equal to the start of Induction Phase treatment, then the medication date will be replaced by the start of Induction Phase treatment. For example, if the medication start date is --/---/2014, and Induction Phase treatment start date is 19/NOV/2014, then the imputed medication start date will be 19/NOV/2014.
- In all other cases, the missing medication day or missing medication month will be replaced by 1.
- In the case that the imputed start date occurs after the medication end date, the medication end date will be used as the start date.
- Incomplete stop date will be replaced by the last day of the month (if day is missing only), if not resulting in a date later than the date of subject's death. In the latter case, the date of death will be used to impute the incomplete stop date.
- In all other cases, the incomplete medication stop date will not be imputed.

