### 11.1 Disposition of Subjects and Discontinuations

Subject disposition summary will be created for the Induction Phase and the Maintenance Phase separately.

For the Induction Phase, the following will be summarized overall and by Induction Phase study treatment for all screened subjects:

- Number of subjects screened
- Number of subjects screen-failed or not treated during Induction Phase
- Number of subjects discontinued during the Induction Phase
- Number and percentage of subjects who completed the Induction Phase treatment
- Primary reasons for treatment discontinuation during the Induction Phase
- Number of subjects completed Induction Phase (overall only)
- Number of subjects completed Induction Phase but not randomized (overall only) and primary reason

Subjects who discontinue Induction Phase chemotherapy due to completion of regimen/randomization to the avelumab or BSC-Only arms will not have the reason presented in the table.

For the Maintenance Phase, the following will be summarized overall and by treatment arm (as randomized) for all randomized subjects:

- Number of subjects randomized
- Number and percentage of subjects randomized but not treated (among those randomized to chemotherapy or avelumab)
- Number and percentage of subjects randomized to the control arm who received BSC-Only
- Number and percentage of randomized subjects still on study treatment
- Number and percentage of randomized subjects who discontinued all study drugs
- Number and percentage of subjects who discontinued any one study treatment and primary reason by study drug, i.e. avelumab, oxaliplatin, 5-FU, capecitabine.
- Number and percentage of subjects who discontinued treatment but are still in follow-up

- Number and percentage of subjects who discontinued the study and primary reasons
- Number and percentage of subjects who re-initiated avelumab treatment
- Number and percentage of subjects who discontinued avelumab treatment after re-initiation and primary reasons
- Number and percentage of subjects in the following analysis sets:
  - Safety-Induction
  - FAS
  - PP
  - Safety-Maintenance
  - HRQoL
  - PD-L1+
- The number of subjects randomized by region and country
- Cross tabulation: subjects randomized (avelumab, oxaliplatin + 5-FU, oxaliplatin + capecitabine, or BSC-Only, Total) versus subjects treated (avelumab, oxaliplatin + 5-FU, oxaliplatin + capecitabine, BSC-Only, or Not Treated).

In addition, the following will be summarized:

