## 16.1 Adverse Events

Treatment-emergent adverse events (TEAEs) are those events with onset dates occurring during the on-treatment period or if the worsening of an event is during the on-treatment period. In this study, there are two on-treatment periods, one for Induction Phase and one for Maintenance Phase.

All analyses described will be based on TEAEs (started during the on-treatment period) if not otherwise specified. The AE listings will include all AEs (whether treatment-emergent or not). AEs outside the on-treatment period will be flagged in the listings.

- **Related Adverse Events:** adverse events with relationship to study treatment (as recorded on the AE eCRF page, Relationship with study treatment = Related) reported by the investigator and those of unknown relationship (i.e. no answer to the question “Relationship with study treatment”).
- **Serious Adverse Events (SAE):** serious adverse events (as recorded on the AE eCRF page, Serious Adverse Event = Yes).
- **Adverse Events Leading to Treatment Discontinuation:** adverse events leading to permanent discontinuation of study treatment (as recorded on the AE eCRF page, Action taken with study treatment = Drug withdrawn).
- **Adverse Events Leading to Death:** adverse event leading to death (as recorded on the AE eCRF page, Outcome = Fatal, as well as AEs of Grade 5).
- **Immune Related Adverse Events (irAEs):** immune related adverse events are identified via customized MedDRA PT queries and additionally classified by medical assessment according to case definition (two level approach). Details are included in [Appendix IV](#).
- **Infusion Related Reactions (IRRs):** IRRs are identified based on a list of MedDRA PTs. The detailed criteria of the timing relationship to infusion are specified in [Table 14](#) of Appendix IV.

Unless otherwise specified, AEs will be summarized by number and percentage of subjects with the AE in the category of interest as described above, by treatment group, primary System Organ Class (SOC) and Preferred Term (PT) and by decreasing frequency based on the avelumab treatment arm.

Each subject will be counted only once within each SOC or PT. If a subject experiences more than one AE within a SOC or PT for the same summary period, only the AE with the strongest relationship or the worst severity, as appropriate, will be included in the summaries of relationship and severity.

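### The AE onset imputation rule uses only the start of randomised treatment and ignores the AE end date, so some Induction AEs can be tabulated in the wrong phase

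*SAP*

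**What the plan says.** **AE rule (SAP section 10, Adverse events).** For a fully missing onset: "If the AE onset date is missing completely, then the onset date will be replaced by the start of randomized treatment". The same date is used when only the day is missing and month and year match randomised treatment start, and when day and month are missing and the year matches. Otherwise: "In all other cases, the missing onset day or missing onset month will be replaced by 1". For the end of the event: "Incomplete stop date will be replaced by the last day of the month (if day is missing only"; the only cap is the date of death. No bullet compares the imputed onset with the end date.

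**Use of the onset date.** SAP 16.1 makes an event treatment-emergent if it starts or worsens in the on-treatment period, and adds: "In this study, there are two on-treatment periods, one for Induction Phase and one for Maintenance Phase". SAP section 10 gives the first window: "For the Induction Phase, the on-Treatment period is defined as the time from the first dose of induction chemotherapy treatment through the earliest of" last Induction dose plus 30 days, the day before new anticancer drug therapy, and the day before Maintenance treatment start. For active treatment in Maintenance, "Treatment Day 1 is defined as the day the first dose of Maintenance Phase study drug was given". SAP Table 8 plans AE tables for both phases.

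**Neighbouring rules.** The medication rule in the same section anchors on the start of Induction treatment and adds: "In the case that the imputed start date occurs after the medication end date, the medication end date will be used as the start date". The rule for subsequent anticancer therapy also checks the end date. SAP section 4.1 records that version 3.0 moved the medication anchor to Induction. It lists no such change for AEs.

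**The concern.** One anchor cannot serve two phases. Three things follow from the text.

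- (a) An Induction AE with a fully missing onset, or a partial onset matching randomised treatment start, is placed on the first day of Maintenance treatment even when its recorded end date is earlier.
- (b) Subjects never randomised belong to the Safety-Induction set but have no randomised treatment start. A fully missing onset then stays missing, because SAP section 10 imputes nothing unless a rule says so, and TEAE status is undefined.
- (c) A partial onset in the month of the first Induction dose is set to the 1st. It can precede that dose and drop out of the Induction TEAEs.

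At stake is the phase attribution of AEs: toxicity of induction chemotherapy shown under avelumab or control, and some Induction events not shown as Induction TEAEs.

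**Working it through.** **Check of the reading.** The rule as read here reproduces both of the SAP's own examples: --/JAN/2015 with start 15/JAN/2015 gives 15/JAN/2015, and --/---/2014 with start 19/NOV/2014 gives 19/NOV/2014.

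**Constructed cases** (dates are illustrative)

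1. First Induction dose 20 Jan 2017, randomised start 20 Apr 2017, onset --/---/2017, AE ended 15 Feb 2017. The year matches, so onset becomes 20 Apr 2017. That is 13 + 31 + 20 = 64 days after the AE ended.
2. First dose 20 Jan 2016, randomised start 18 Apr 2016, onset --/APR/2016, AE ended 5 Apr 2016. Onset becomes 18 Apr 2016, 13 days after the end.
3. Same subject, onset --/JAN/2016. Onset becomes 1 Jan 2016, 19 days before the first dose.
4. Never randomised, onset fully missing: no date can be assigned.

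**Shares per affected AE.** These apply to Induction AEs with an incomplete onset that ended before randomised start.

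Inputs and assumptions:
- Induction lasts 12 weeks, or 84 days (Protocol 5.1.2.1). Re-baseline takes up to 10 days (Protocol 7.1.3), and treatment starts within 4 days of randomisation (Protocol 7.1.4). Randomised start is taken as g = 85 days (84 + 1) to 99 days (85 + 10 + 4) after the first dose.
- Assumed: each first-dose date over four calendar years is equally likely; onset is uniform from first dose to the day before randomised start; the end is uniform from onset to that same day.

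With first dose d, randomised start r = d + g and true onset o:
- Fully missing: imputed to r in every case.
- Year-only: r if year(o) = year(r), otherwise 1 January of year(o).
- Day-missing: r if the month and year of o and r agree, otherwise the 1st of o's month. This is before d if o lies in the month of d and d is not the 1st.

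| Onset | To Maintenance start | Before first Induction dose | Kept between the two |
|---|---|---|---|
| Fully missing | 100% | 0% | 0% |
| Year-only | 88.2% (g = 85), 87.3% (92), 86.3% (99) | 11.8%, 12.7%, 13.7% | 0% |
| Day-missing | 17.3%, 16.0%, 14.9% | 17.3%, 16.0%, 14.9% | 65–70% |

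**With the fix below.** If the end date is complete, the first two columns fall to 0%. If the end date lacks its day, an end in the month of randomised start is moved to month end, which is not before that start, so the Maintenance default remains. The residual share in Maintenance is then 40–44% (fully missing), 37–41% (year-only) and 15–17% (day-missing, unchanged). In the constructed cases, case 1 becomes 20 Jan 2017 and case 2 becomes 1 Apr 2016, before its end date and before randomised start. Case 3 becomes 20 Jan 2016 if its end date is before 18 Apr 2016.

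**The case against.** **Caution.** Defaulting an unknown onset to randomised start is a cautious convention for Maintenance. This stands where the end date is missing or uninformative, and the fix keeps it there. It fails where a recorded end date precedes that start, because the data then exclude a Maintenance onset.

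**Other provisions.** It is tempting to call this the only rule that governs AE dates. SAP 16.1 does not support that. Consecutive records of one event that do not worsen take the first record's start, with the TEAE flag adjusted, and worsening within a window also makes an event treatment-emergent. Both narrow the effect; neither helps an AE held in a single record.

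**Randomised but untreated subjects.** A reader might infer that they too have no reference date. SAP 11.1 expects such a group: "Number and percentage of subjects randomized but not treated (among those randomized to chemotherapy or avelumab"). The Exposure rule in SAP section 10, however, lets the randomisation date stand in for a missing first Maintenance dose date. That is probably meant for unrecorded dates rather than doses never given, so the point is arguable for this group. It is firm only for the never randomised.

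**Frequency.** Protocol 7.4.1.2 asks for complete AE data with onset and resolution dates, so the percentages may apply to very few records. This stands. Nor is 85–99 days a bound: dose delays are allowed in Induction, and the schedule footnotes place Re-baseline 10 to 1 days before the first Maintenance administration, so adding 4 days may count some time twice.

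**Visibility.** Imputed values are flagged in listings. That makes the records traceable but does not correct the tables.

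**Conclusion.** The rule is wrong as written for AEs whose end date precedes randomised treatment start, and it has a gap for never-randomised subjects. The early dating of partial onsets in point (c) is real but weaker, since moving them has an equal cost in screening time (see the fix).

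The shares above are conditional on an incomplete onset and on the stated uniform assumptions. With no count of incomplete dates, the effect on any table cannot be sized and may be small.

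A reader might go further and infer that the Maintenance safety comparison is unreliable or that a hypothesis test is affected. The documents support neither. Safety is summarised descriptively (Protocol 8.5.5, SAP 16), the same rule applies in both arms, and no efficacy endpoint uses these dates. This should be corrected because the contradiction is plain and the repair is cheap, not because a large effect has been shown.

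**What to change.** For incomplete AE onsets in SAP section 10:

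1. Keep the randomised-start default (BSC-only: the Week 1 Day 1 visit) only if the AE end date, after the existing stop-date rule, is missing or not before that start.
2. If the end date is before that start, or the subject has no randomised treatment start, apply the medication logic with the first Induction dose as anchor: that date for fully missing onsets and for partial onsets matching its month and year (or year); otherwise set the missing part to 1.
3. If the imputed onset is after the AE end date, use the end date as onset.

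Using the first Induction dose for other partial onsets that match its month or year is optional. For day-missing onsets, anchoring on that dose recovers 14.7 Induction days per subject on average and exposes 14.7 screening days. It is a gain only if AEs are more frequent on chemotherapy than in screening, which the documents do not state. Without this option, some early partial onsets with a missing or late end date will still precede the first dose.

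**Cost.** A few lines of SAP text and derivation code, and no new data. AEs are collected from consent, so some screening AEs with incomplete onsets that ended on or after the first Induction dose would count as Induction TEAEs. With onsets uniform over a 28-day screening window, the ceiling is about 52% of day-missing and 96% of year-only screening onsets, plus fully missing onsets that meet the end-date condition. The 96% has two parts. In 69–73%, first dose and randomised start fall in the same year, and step 2 moves the onset. In 23–27%, randomised start falls in the next year, and the onset moves under the optional extension, or under step 2 if the end date is early enough. For randomised subjects, the fully missing onsets and the 69–73% moved by step 2 would otherwise be miscounted as Maintenance TEAEs.
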